7.4. Incidental Findings by MRI

The study subjects to be recruited for this study are generally healthy. Sometimes, however, a few incidental abnormalities may be found in study subjects, such as brain tumors, vascular lesions, moderate to severe white matter lesion load, and other neuroradiological abnormalities that would preclude subjects from being included in the analysis, or that are clinical abnormalities requiring follow-up. These subjects will be advised to see their physicians for formal assessment. [name] is a board-certified neurologist at MCW. He will consult with the subjects in such cases.

7.5 Magnetoencephalography (MEG) Risks:

There are no health risks associated with MEG, but there is some risk of discomfort. During MEG recording, due to restriction of head movements and being in a small room, some people may experience an unpleasant feeling of confinement or discomfort from sitting still for a long time.

7.6. Subject Safety

Due to the duration and low dose of stimulation, we anticipate this study to present minimal risk to subjects. We do not expect frequent or severe AEs to occur. Subjects will be instructed to call the study site concerning any adverse events or illnesses that may occur. The DSMB will review the frequency and severity of any AEs. Stopping rules will be invoked for the subject and study if AEs are reported above the 5% threshold. Subject safety will be closely monitored during the study period, and individual participation in the study may be

suspended or terminated pending resolution of the AE. Safeguards to ensure subject confidentiality will consist of maintaining records in a locked cabinet in a locked room in the Department of Neurology research offices. All computers are password protected and encrypted to further ensure safety.

7.7. Data

The time frame for data analysis will be at the time point when 50% of subjects have been recruited. AE data analysis will be performed every 6 months. Plans for unexpected problems involving risk to participants or others will consist in notification of the principal investigator in order to activate appropriate medical or professional intervention as needed.

7.8. Efficacy

Given the pilot nature of this study, two feasibility outcomes will be included: Consent rate and treatment completion rate. Only four patients are sufficient to calculate a 90% exact binomial confidence interval of (.56, 1) if all four are observed to complete treatment. Thus, this sample size would be large enough to potentially exclude completion rates of 56% or lower. The collection of pilot data from this study will provide initial estimates of the variability and the effect sizes. This information will then be used for the more formal calculations of power and sample size necessary to conduct a future trial.

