Efficacy Assessments	(i) Consent rate and treatment completion rate (ii) Statistically significant differences between baseline and post- tDCS stimulation performance on a series of language metrics.
Unique Aspects of this Study	This is the first study to evaluate the efficacy of HD-tDCS for the treatment of language deficits of lvPPA, a neurodegenerative and progressive condition with no known effective treatment. It would also be the first study to access whether HD-tDCS can increase brain functional connectivity and regulate abnormal patterns of neuronal frequencies and synchronizations in this patient population.

Table of Contents

1. Study Objectives	5
2. Background and Significance	6
3. Rationale	7
4. Study Design	8
5. Study Visits and Procedures	9
6. Data Management	15
7. Data Safety Monitoring Plan	16
8. References	21

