4.3. Subject Recruitment

To enroll a total of 20 study participants, we anticipate pre-screening and approaching about 50 IvPPA patients who are seen in the MCW Neurology clinics and the MCW Geropsychiatry clinic for standard care. These patients will range in age from 45–85 years. Recruitment efforts will be conducted exclusively in the MCW Neurology and Geropsychiatry clinics initially but may be expanded to include the greater metropolitan Milwaukee, WI area if needed. The Medical College of Wisconsin (MCW) Dementia Research Team has extensive experience recruiting patients from the clinic and the Milwaukee community, using flyers, press releases, and community presentations.

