Define $\widetilde{LG}(s, g, t) \equiv Res(s, g, t)$. We will test the residuals $\widetilde{LG}(s, g, t)$ using a *three-factor crossed-nested* ANOVA, with fixed factors *group* and *time*, and random factor *subject* nested within *group*. We will test for group and time main effects, as well as the group \times time interaction. If we find significant main effects or interactions, we will perform post hoc procedures to determine which time and group combinations are significantly different.

6.4. Functional-Connectivity Changes Due to Stimulation. We will use the well established Human Connectome Project (HCP) fMRI processing pipelines implemented by [name] group at MCW, which include state-of-the-art noise removal, spatial normalization, and surface-based cortical parcellation methods.

Functional connectivity matrices will be computed by first parcellating the brain into multiple regions of interest (ROI), averaging the preprocessed fMRI signal over each ROI, and then computing the Z-transformed correlation coefficient between every ROI pair. The functional connectivity of a number of different parcellation schemes will be examined. This includes anatomical atlas based parcellation, such as the Harvard Oxford atlas, a validated probabilistic atlas implemented in FSL that divides each hemisphere into 56 regions corresponding to portions of cortical gyri and subcortical gray matter nuclei; combined anatomical and functional parcellation of regions that tend to co-activate during resting state, as implemented in Statistical Parametric Mapping (Tzourio-Mazoyer, N., et al., 2002) and purely functional delineations such as the Crad-200, a constrained spectral clustering of resting state fMRI data into 200 parcels encompassing both cortical and subcortical regions, and a high model order Independent component analysis (ICA), as advocated by HCP investigators. Targeted exploration of connectivity driven by current understanding of the pathophysiology of IvPPA will also be pursued.

We will employ age, years of education, gender, and gray matter (GM) volume as time-invariant covariates to obtain residual variables to determine LFC changes due to stimulation. We will model the LFC as a function of these nuisance regressors, using the following multiple linear regression equation, and retain the residuals as $LFC_{Res}^+(s, t)$ for further analysis:

$$LFC(s, t) = \beta_0 + \beta_1 Age(s) + \beta_2 Edu(s) + \beta_3 GM(s) + \beta_4 Gender(s) + Res(s, g, t)$$

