6.7. Expected Results, Deliverable, and Problems

Through this study, we expect to realize two goals: **Scientifically**, we will demonstrate that active HD-tDCS can increase language-network functional connectivity and improve abnormal patterns of resting state neuronal frequencies and synchronizations. **Clinically**, we expect that the changes in network activity after the 2-week stimulation period will lead to language improvement. This study can provide conceptual proof for a rehabilitation intervention. In addition, this study will provide information and address the power of adequate enrollment, protocol adherence, subject retention, and safety for future pilot and pivotal trials.

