6.8. Data Sharing

Subjects will provide written informed consent via an addendum consent form, noting their permission for the study team to share all data collected throughout their participation in the study with UW-Madison collaborator

[name] in the Department of Communication Sciences and Disorders and her team. [name] and her team will analyze the study data and provide statistical support to the MCW study team.

The following data will be sent to [name] in a secure and protected manner:

- Study ID number
- Dates of visits and consent
- Demographic information, such as age, year of birth, sex, handedness, race, ethnicity, educational history, and childbearing potential
- Medical history, such as medical/neurological diagnoses and medications
- Randomization information
- Adverse events
- TMS Neuronavigation data
- Performance on cognitive and language tests
- Voice recordings and speech samples
- Images from MRI scan
- Recordings from MEG scan

Once data analysis and statistical support are complete, [name] send results back to the study team, where they will be stored for the duration of the study.

The data we provide will not contain any information that can directly identify subjects.

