7.10. Feedback Mechanism

Evaluation and response to any subject complaints will be reviewed by the DSMB. The IRB will be notified of protocols violations and emergence of unexpected AEs at any time during the study. In addition, a report by the DSMB will be provided to the IRB at the end of the study.

Table 1. Schedule of Study Procedures.

Period	Screen	Treatment Period 1			Assessment 1 ^{ab}	Treatment Period 2			Assessment 2 ^b
Visit	-1	1	2-9	10	11	12	13-20	21	22
Visit window	-3 months	-3 months	+1 month	+1 month	±1 month	-3 months	+1 month	+1 month	±1 month
Informed Consent	X								
Inclusion/Exclusion Criteria	X								
Demographics	X								
Medical History	X								
MRI Safety Screening	X					X			
Language Battery	X ^j		X ^{fh}		X	X ⁱ		X ^{fh}	X
Training Tasks		X	X	X	X	X	X	X	X
fMRI ^c		X ^g		X ^h		X ⁱ		X ^h	
MEG		X ^g		X ^h		X ⁱ		X ^h	
Randomization		X							
tDCS		X	X	X		X	X	X	
Phone Follow Up/					X				

Visit Reminder ^d									
Adverse Events ^d		X	X	X	X	X	X	X	X
TMS Neuronavigation (for stimulation planning) ^e	X ^j								

^a Assessment 1, Visit 11 occurs in the middle of the 16-week washout period.

^b In the case of early termination, Assessment Visit procedures will be performed.

^c Subjects will undergo mock scanner training. If a subject has been previously engaged in MRI as part of research, the subject may be excused from mock scanner training.

^d Phone Follow-Ups will be conducted during the 16-week washout period. They will be conducted 4 weeks post Treatment Period 1, 1 week prior to Assessment Visit 1, and 1 week prior to Treatment Period 2. AE review will be completed, and reminders for upcoming visits provided.

^e TMS Neuronavigation will occur at the investigators discretion.

^f Language assessment sessions will be conducted after Treatment periods 1 and 2 (visit 10 for period 1 and visit 21 for period 2).

^g These procedures can occur on 2 or more separate days, but within 3 months before the first treatment session of Treatment Period 1. They may overlap with Visit -1 procedures.

^h These procedures can occur on 2 or more separate days, but within 1 month after the last treatment session of Treatment Period 1 or the last treatment session of Treatment Period 2.

ⁱ These procedures can occur on 2 or more separate days, but within 3 months before the first treatment session of Treatment Period 2.

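### Do the consent and completion rates need formal definitions and a SAP analysis before they can be reported?

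*Protocol*

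**What the plan says.** The protocol summary puts "Consent rate and treatment completion rate" first under Efficacy Assessments. Section 7.8 repeats the two rates, giving the pilot character of the study as the reason: "two feasibility outcomes will be included: Consent rate and treatment completion rate". It then supplies one illustration: "Only four patients are sufficient to calculate a 90% exact binomial confidence interval of (.56, 1) if all four are observed to complete treatment". From this it infers that a completion rate of 56% or less could potentially be ruled out.

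Three other places bear on the rates:

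- Section 6.7 says the study will "address the power of adequate enrollment, protocol adherence, subject retention, and safety for future pilot and pivotal trials".
- Section 4.3 gives the recruitment expectation: to enrol 20, "we anticipate pre-screening and approaching about 50" patients. It does not call this a consent rate.
- Section 6.8 lists "Dates of visits and consent" among the data held.

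The SAP describes item-level language analyses within each participant (Cochran's Q, McNemar, Wilcoxon). It says the sample was too small for group-level testing, does not give the number enrolled, and mentions neither feasibility rate.

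**The concern.** Two outcomes promised in the protocol have no analysis in the SAP, and their names can be read in more than one way. Completion might mean finishing one 10-session period, finishing both periods, or attending Visit 22. Consent might be counted out of everyone pre-screened, everyone approached, or only those eligible.

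The timing adds to the worry. The protocol planned a group analysis of two 10-subject groups (section 6.3: "We will test for group and time main effects"). The SAP, dated July 2023 and written in the past tense, abandons it because of sample size without saying whether recruitment, refusal or dropout was the cause. If definitions were chosen once the data were known, the more flattering one could be picked, and a later trial could be planned on a retention figure that is too high. The 4-of-4 illustration offers no protection, because it describes only the case in which nobody drops out.

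**Working it through.** **1. The printed interval.** Inputs from section 7.8: n = 4, x = 4, 90%, exact binomial. When x = n, the exact lower limit solves p^4 = α.

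- All 10% in the lower tail: 0.10^(1/4) = .5623. Check: .5623^4 = .09997.
- 5% in each tail: 0.05^(1/4) = .4729.

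The printed .56 is therefore a one-sided 90% limit. The upper end of 1 fits that reading, since there is no room above 4/4. The protocol makes the statement conditional on all four completing, and on that condition it is correct.

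**2. How far it depends on the best case.** With 3 of 4 the one-sided limit falls to .32 (two-sided 90%: .25 to .99). If true completion were 80% (an assumption), 4 of 4 would occur with probability 0.8^4 = .41.

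**3. The planned 20.** Exact lower limits:

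| Completers | One-sided 90% | Two-sided 90% |
|---|---|---|
| 14/20 | .533 | .492 |
| 15/20 | .585 | .544 |
| 16/20 | .639 | .599 |
| 18/20 | .755 | .717 |

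To exclude 56% takes 15 completers one-sided or 16 two-sided. At an assumed true rate of 80% these have probability .80 and .63. The choice of side shifts the limit by about .04 in each row; it does not change the observed proportion.

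**4. What completion can mean.** Protocol section 4.1 and the randomization section say that every participant receives sham in one period and stimulation in the other. Table 1 shows no tDCS at Visit 22, so that visit is follow-up. Finishing Period 1 alone is 10 of the 20 sessions. Both periods is therefore the natural reading. The alternative matters only if someone adopts it: with assumed counts of 19/20 for Period 1 and 16/20 for both, the rates are .95 (.78, 1.00) and .80 (.60, .93), two-sided 90%.

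**5. What consent can mean.** Take 20 consenting and 50 approached from section 4.3, and assume 0, 10 or 20 of the 50 were ineligible:

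- 20/50 = .40 (.28, .53)
- 20/40 = .50 (.36, .64)
- 20/30 = .67 (.50, .81)

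The spread is wide, but it comes entirely from the denominator. A flow of counts (approached, eligible, consented) gives all three.

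**6. Would the two rates explain a small sample?** Not by themselves. Suppose only four eligible patients could be approached, and all four consented and completed. Both rates would be 1 and the sample would still be 4. The counts explain a shortfall; the proportions need not.

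**7. Absence from the list in section 1.3.** That list is introduced as the measures used to test the study hypothesis, which concerns language, connectivity and oscillations. Feasibility rates do not test it, so leaving them out is not a contradiction.

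**The case for a change.** The strongest case for a change is that feasibility is what a pilot is for. Section 7.8 gives that very reason for including the rates. They can be calculated however few patients were enrolled, so the SAP's reason for dropping group testing does not cover them. A proportion still needs a numerator and a denominator, and one SAP paragraph would cost little. Table 1 adds a complication: "In the case of early termination, Assessment Visit procedures will be performed". Attendance at an assessment therefore does not by itself show that treatment was finished.

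Part of this stands. The documents do not say how missed sessions count towards completion, do not settle the consent denominator, and do not mention a log of patients approached. The side of the .56 limit is unlabelled.

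These points do not add up to a fault in the plan. No stated rule produces a wrong result. Treatment dates by period separate those who finished from those who left early, so the early-termination assessment need not mislead. Because the SAP was written after the fact, new definitions in it would be post hoc and would not prevent selective choice; showing the counts by step does that, and needs no amendment. Labelling .56 as one-sided would be tidier, but the figure is correct and no decision rests on it.

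**Conclusion.** No change follows. This is missing detail of a kind that analysts fill sensibly: consented patients over those approached or eligible, and participants finishing both periods over those randomised, each with its counts and an exact interval. The protocol's commitment to report the two rates still holds, since the SAP is silent on them and does not withdraw them.

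The largest effects shown here, .80 against .95 for completion and .40 against .67 for consent, rest on assumed counts and on a report that gives a rate without its denominator. The printed .56 is right as a one-sided 90% exact limit. The item-level language analyses do not use either rate.

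This conclusion assumes that the rates are reported with their counts. If no record of approaches was kept, the consent rate could not be calculated, and wording added to the SAP now would not recover it.

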Secondary Objectives	(ii) evaluate the effects of HD-tDCS on functional connectivity using functional Magnetic Resonance Imaging (fMRI), and (iii) elucidate its effects on spontaneous neuronal oscillatory patterns using Magnetoencephalography (MEG).
Endpoints	
 • Primary outcome measurements: Language performance changes as assessed at baseline and after tDCS stimulation procedures (time frame: 2 weeks). • Secondary outcome measurements: (ii) Changes in brain functional connectivity as assessed at baseline and after tDCS stimulation (time frame: 2 weeks) (iii) Changes in abnormal patterns of neuronal frequencies and synchronizations as assessed at baseline and after tDCS stimulation procedures (time frame: 2 weeks).

Study Design	
This clinical utility study is a randomized, double-blind, sham-controlled trial in which stimulation or sham will be administered to 20 subjects over the age of 45 years, with the order of treatments counterbalanced in a within-subject crossover design. Stimulation and sham sessions last 20 minutes and occur for 10 days over a 2-week period.
 
The study consists of Pre-screening (Visit –1), Baseline (Visit 1), a 2-week Treatment Period (Visits 1-10), a 16-week Washout Period, an Interim Assessment (Visit 11), a second 2-week Treatment Period (Visits 12-21), and a Final Assessment (Visit 22).

Study Agent/ Intervention Description	tDCS and sham stimulation sessions lasting 20 minutes at a current intensity of up to 2mA in the targeted cortical tissue
Number of Subjects	20
Subject Participation Duration	28 weeks: 2 weeks of tDCS/sham, followed by a 16-week washout, followed by 2 weeks of tDCS/sham, followed by an 8-week final assessment.
Duration of Follow up	None
Estimated Time to Complete Enrollment	18 months
Statistical Methodology	The collection of pilot data from this study will provide initial estimates of the variability and the effect sizes. This information will then be used for the more formal calculations of power and sample size necessary to conduct a pivotal trial. All future statistical testing will use repeated measures ANOVA once a large enough sample is reached.
Safety Assessments	Data safety monitoring board meetings will be scheduled to monitor progression of the study and review drug adverse events

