1.2. Objectives

To determine whether active HD-tDCS targeting the dominant posterior TPC can improve language performance, increase language network functional connectivity, and improve abnormal patterns of resting state neuronal frequencies and synchronizations.

Specific Aim 1. Determine changes in language performance after 10 HD-tDCS stimulation sessions (QD) lasting 20 minutes at a current intensity of up to 2mA in the left TPC in a randomized, double-blind, sham-controlled, within-subject cross-over study with 20 lvPPA subjects ages 45 years and greater.

Specific Aim 2. Determine the effects of the conditions described in Specific Aim 1 on the resting state Language network-level changes in left TPC functional connectivity between the conditions described in Specific Aim 1.

Specific Aim 3. Determine the effects of the conditions described in Specific Aim 1 on the neuronal frequency distribution and connectivity measures associated with the left TPC as assessed by MEG.

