4. STUDY DESIGN

4.1. Overall Design

This study will test our hypothesis that HD-tDCS will improve performance on language tasks by increasing functional connectivity and by regulating abnormal neuronal oscillatory patterns. The language performance and functional connectivity changes will be determined in a randomized, double-blind, sham-controlled crossover manner, in which a stimulation of up to 2mA in the targeted cortical tissue or sham is administered to 20 IvPPA subjects age 45 years and older. The order of treatments is counterbalanced in a within-subject crossover design, as illustrated in Fig. 2 below. In brief, study participants will receive sham during one treatment period and stimulation during the other treatment period.

Figure 2. Study Design and tDCS Treatment Protocol

The Screening Visit includes medical history, Language Assessment battery, MRI safety screening, and TMS Neuronavigation. Visit 1 (Baseline) will include fMRI and MEG. Additionally at Visit 1, and for 9 additional days in a two-week period (Tx Period 1), each subject will undergo real stimulation or sham and simultaneous word and non-word reading and repetition tasks. At the end of Tx Period 1, a 16-week washout period begins. After the first 8 weeks of the 16-week washout period, subjects return for Assessment Visit 1 where they receive the Language Assessment battery, including the reading and non-word repetition tasks tested at baseline, and 'trained' during each of the stimulation sessions. After the 16-week washout period, Tx Period 2 begins. Subjects undergo stimulation or sham and the simultaneous word and non-word reading and non-word repetition tasks for 10 days over a two-week period. Eight weeks after the end of Tx Period 2, subjects receive the Language Assessment Battery at Assessment Visit 2, which is the last study visit.

An unblinded member of the study team having no contact with the study subjects will randomize them to the treatment conditions, while the language assessment battery of tests will be delivered by a blinded member of the study team. The language training exercises used during each tDCS session as well as the tDCS intervention itself will be delivered by a blinded, qualified and formally tDCS-trained member(s) of the study team.

Data safety is monitored by three data safety monitoring board (DSMB) members who are not related to the study.

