Study Title: High-Definition Transcranial Direct Current Stimulation (HD-tDCS) in logopenic variant Primary Progressive Aphasia (lvPPA): Effects on Language and Neural Mechanisms.

NCT: NCT03805659

Date of document: July 06, 2023

Statistical Analysis:

- The small sample size in this study precluded group-level statistical analysis.
- Instead focused on a within subject item-level analysis.
- Language performances in each trial period were assessed separately to help control for potential carryover effects and for effects of progressive neurodegeneration.
- The Cochran's Q test was used to determine if there were any differences on a dichotomous variable across the three-trial period timepoints.
- Because the same assessment list/version was used within a given stimulation condition per participant, we coded "right" and "wrong" answers to an individual assessment item as our dichotomous variable.
- If the preliminary Cochran's Q test demonstrated a significant difference ($p<0.05$) between participant responses in a language assessment between two timepoints, a follow-up non-parametric pairwise comparison between the baseline and timepoint list was tested using a McNemar test with a false discovery rate correction (Sheppard et al., 2021; Hung et al., 2017; Tsapkini et al., 2015).
- While the Cochran's Q and post-hoc McNemar test allowed us an objective comparison between timepoints within conditions for each individual participant, we utilized a Wilcoxon-signed rank test to assess participant performance changes between aHD-tDCS and sHD-tDCS (ex: aHD-tDCS T0-T1 percentage change from baseline vs. sHD-tDCS T0-T1 percentage change from baseline). This assessment would allow us a more quantitative direct comparison between treatment conditions on an individual participant (Sheppard et al., 2021). The statistical analyses described were performed using SPSS version 27.0 (IBM, Armonk NY). A p-value of <0.05 was used to describe statistical significance.

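### Is the 90% exact interval of .56 to 1 for four completers out of four wrong, or based on the wrong sample size?

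*Protocol*

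**What the plan says.** Section 7.8 of the protocol names two feasibility outcomes for this pilot, the consent rate and the treatment completion rate. The Efficacy Assessments row of the Protocol Summary lists the same pair. For completion, section 7.8 gives the only precision figure in the documents: "Only four patients are sufficient to calculate a 90% exact binomial confidence interval of (.56, 1) if all four are observed to complete treatment". It then concludes that "this sample size would be large enough to potentially exclude completion rates of 56% or lower". The section goes on to say that the pilot data will supply variability and effect-size estimates for sizing a later trial.

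The planned enrolment is stated consistently elsewhere:

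- Protocol Summary, Study Design: "stimulation or sham will be administered to 20 subjects over the age of 45 years"
- Section 1.2, Specific Aim 1: "sham-controlled, within-subject cross-over study with 20" subjects
- Section 4.1: "in the targeted cortical tissue or sham is administered to 20" subjects
- Section 4.3: "To enroll a total of 20 study participants"

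Section 6.2 also works with two groups of ten. The SAP does not mention the completion rate. Its remark that "The small sample size in this study precluded group-level statistical analysis" concerns the language analysis and gives no number enrolled.

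**The concern.** Two things look wrong in section 7.8.

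First, an interval printed with two endpoints and called 90% exact is usually taken to be the equal-tailed Clopper-Pearson interval, with 5% in each tail. For 4 of 4 that interval starts at .47. On this reading .56 belongs to an 80% interval, and completion rates between 47% and 56% would not be excluded as the text claims.

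Second, the sentence that draws the conclusion refers to four patients as the sample size, while the rest of the protocol plans 20. If four were the real basis, the feasibility objective would rest on a fifth of the intended enrolment. The precision to be expected from 20 patients is given nowhere.

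At stake is how one of the two feasibility outcomes is stated, and what a planner of the next trial could take from it. Section 6.7 says the study should inform enrolment, adherence and retention in later trials.

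**Working it through.** **Inputs.** Section 7.8 gives n = 4, x = 4, level 90%, method exact binomial and printed limits .56 and 1. The planned size of 20 comes from the Protocol Summary and sections 1.2, 4.1 and 4.3. Completer counts below 20 of 20 are assumptions for illustration; the documents give none.

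**Step 1: reproduce the printed figure.** When everyone completes, the exact lower limit solves p^n = a, where a is the lower-tail area, and the upper limit is 1.

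- All 10% in the lower tail: p = 0.10^(1/4) = 0.5623. This is the printed .56.
- 5% in the lower tail (equal-tailed): p = 0.05^(1/4) = 0.4729.

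The protocol's number is therefore the one-sided 90% exact bound, correctly calculated. The two conventions differ by 0.5623 − 0.4729 = 0.089, or about nine percentage points.

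**Step 2: is the one-sided interval valid at 90%?** The procedure that always reports the lower bound up to 1 has a minimum coverage of 90% at n = 4. With 4 of 4 the upper endpoint is 1 under either convention, so writing the bound as (.56, 1) does not misstate it.

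**Step 3: does the conclusion hold?** If the true completion rate were 56%, the chance that all four complete would be 0.56^4 = 0.0983. This is below 0.10, so 56% and anything lower is excluded at one-sided 10%.

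**Step 4: what would 20 patients give?**

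| Completers | One-sided 90% exact lower bound | Equal-tailed 90% exact interval |
|---|---|---|
| 4 of 4 | .562 | .473 to 1 |
| 20 of 20 | .891 | .861 to 1 |
| 18 of 20 (assumed) | .755 | .717 to .982 |
| 16 of 20 (assumed) | .639 | .599 to .929 |

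With full completion the conventions differ by only 0.8913 − 0.8609 = 0.030 at n = 20. A rate of 56% would be excluded one-sided if at least 15 of 20 complete (lower bound .585; for 14 it is .533). Under the equal-tailed convention it takes 16 (.599; for 15 it is .544).

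**Step 5: if fewer than 20 were enrolled.** The number enrolled is not stated. The lower limits for full completion, one-sided and then equal-tailed, are .68 and .61 at n = 6, .75 and .69 at n = 8, .79 and .74 at n = 10, and .86 and .82 at n = 15. All are above the four-patient figure under the same convention.

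**The case for a change.** The strongest case for a change is that a one-sided convention is sound only if it is used whatever the outcome. Suppose an analyst used equal-tailed limits in general but moved to one-sided limits when none or all of the four complete. Just below p = 0.5623 the coverage would be 1 − 0.5623^4 − 0.4377^4 = 1 − 0.1000 − 0.0367 = 0.863, which is no longer 90%. On this argument the convention should be written down before the result is known. The wording also treats four as the sample size and never links it to 20, and the correction would take only a sentence or two.

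Part of this stands. The label is missing, and no precision is stated for the planned enrolment. But nothing in the protocol suggests switching between conventions. Among the exact limits, only the one with the full 10% in the lower tail reproduces .56, so the convention can be recovered from the printed number. (A mid-P limit has the same value, but mid-P is not an exact method.) The single use made of the interval is one-directional, which suits a lower bound. Replacing .56 by .47 would exchange one valid convention for another. On the sample size, the opening words of the sentence present four as enough for a first statement about completion, and every passage that sets enrolment says 20.

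**Conclusion.** The concern does not call for a change. The printed limit is correct as a one-sided 90% exact bound (0.562), the exclusion claim holds at that level (0.098 against 0.10), and the four-patient example is compatible with a plan for 20. The equal-tailed alternative at 4 of 4 is .47. The gap of about nine points shrinks to three at 20 of 20, where the bounds are .89 and .86.

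No decision rule, efficacy analysis or safety rule depends on 56%. Completion is a descriptive pilot outcome, and formal sizing is left to a future trial. Once the data are in, the result will be a count of completers among those enrolled, and its interval will replace the four-patient illustration. An analyst would sensibly state the convention alongside that interval.

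This conclusion rests on two readings: that .56 was meant as a lower bound, which the arithmetic and its use support, and that four is a minimum case, which the consistent target of 20 supports. If the second reading were wrong, the four-patient example would still not overstate what full completion at a larger enrolment would show.
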